### 6.2 STUDY AIMS

Purpose: This is a prospective, interventional study to evaluate the effectiveness of FUE in reducing severity score of mild to moderate HS.

#### Primary objective.

1. To evaluate the effectiveness of FUE in reducing severity score of mild to moderate HS.

#### Secondary objective.

2. Comparing scores of HS severity assessments between intervention and control group at week 6, 12 and 24 after follicular unit extraction.
3. Comparing scores of HS severity assessments before and after follicular unit extraction on the treated site at week 6, 12 and 24 after follicular unit extraction.
4. To compare the number of disease flares between intervention and control group over 24 weeks.
5. To determine if specimens contain HFs, sebaceous glands, apocrine glands and eccrine glands on histopathology.

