## 2. STUDY SYNOPSIS

Provide brief information

Title:	Hidradenitis suppurativa treated with follicular unit excision: A prospective controlled pilot study
Short Title:	Hidradenitis suppurativa treated with follicular unit excision: A prospective controlled study
Design:	Open-label, interventional
Study Centres:	Sinclair Dermatology, Melbourne Australia
Hospital:	
Study Question:	How effective is follicular unit excision for the treatment of mild-moderate hidradenitis suppurativa?
Study Objectives:	
Primary Objectives:	The study's primary objective is to determine change in several hidradenitis suppurativa assessment scores score throughout follow-up visits in the first 24 weeks after follicular unit excision
Secondary Objectives	
 
i) To compare the changes in Hidradenitis Suppurativa assessment scores between intervention and control groups up to 24 weeks and on the treated sites before and after follicular unit extraction
 
ii) To compare the number of disease flares between the treated and control groups for 24 weeks after treatment
 
iii) To determine if specimens contain hair follicles, sebaceous glands, apocrine glands and eccrine glands on histopathology
 

Key Inclusion Criteria:	
 
i) Patients aged <math>\geq 18</math> years with hidradenitis suppurativa
 
ii) Mild-moderate hidradenitis suppurativa defined by Hurley stage 1 up to 2A
 
iii) Minimum diagnosis of 3 months prior to baseline
 
iv) Active hidradenitis suppurativa present for <math>\geq 3</math> months from initial diagnosis
 

Key Exclusion Criteria:	
 
i) Current treatment with systemic antibiotics, retinoids, immunosuppressants or biologic agents at discretion of the investigator
 
ii) Extensive scarring
 
iii) Absence of terminal hairs in target areas
 
iv) Previous laser hair removal in target areas
 
v) Pregnant or lactating women
 

Number of Planned Participants :	24
Investigational procedure:	Follicular unit excision using 0.8 mm Ertip® punch
Data analysis	The primary objective is to evaluate the efficacy of follicular unit excision in the treatment of adults with mild to moderate hidradenitis suppurativa. The primary analysis will be conducted to assess the primary and secondary endpoints once all participants have completed the Week 24 visit.
Safety considerations:	

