### 6.3 OUTCOME MEASURES

1. Hidradenitis suppurativa clinical response score (HiSCR)
2. Hidradenitis suppurativa – Physician’s global assessment (HS-PGA)
3. International Hidradenitis Suppurativa Severity Score System (IHS4)
4. Pain score (NRS30)
5. Number of abscesses and nodule counts at each visit
6. Number of flare ups as well as location of flare ups

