#### 6.4.1.8 HIDRADENITIS SUPPURATIVA SEVERITY ASSESSMENT

As part of standard routine care, participants will have the Hurley Stage of their HS, nodule count and abscess count documented at baseline. This is part of standard routine care to assess whether treatment is effective, and it will also allow us to calculate the hidradenitis suppurativa clinical response (HiSCR). HiSCR is defined as a  $\geq 50\%$  reduction in inflammatory lesion count (abscesses and inflammatory nodules), and no increase in abscesses or draining fistulas when compared with baseline. Participants will also have their hidradenitis suppurativa-physician's global

assessment (HS-PGA) and International Hidradenitis Suppurative Severity Score System (IHS4) score documented in follow-up visits. Pain will be assessed using the numerical scale 30 (NRS30) pain score (See Appendix 1).

These assessments will be done at week 0, week 6, week 12 and week 24.

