## 6.7 STUDY METHODOLOGY

Participants will be taken to the procedure room. Local anaesthesia will be injected into diseased hair-bearing area on affected axillae or groin on both sides. FUE will be performed by the investigator (who is experienced in FUE) using 0.8/0.9/1.0 mm Ertip® punch. The extracted hair follicular unit samples will be analysed histologically to confirm complete removal of the pilosebaceous units. Specimens are not kept for future analysis as they will be discarded.

At each study visit, the dermatologist will count the number of abscesses and nodules (as part of standard routine care) and will document this in their medical record. This will help to also score the HiSCR, IHS4, HS-PGA4 and participants will ask to rate their pain using the numerical pain score. Scoring will be done by the principle investigator as well as another dermatologist at Sinclair Dermatology.

Participants will be given a sheet (Appendix 3) where they can complete a diary of whenever they have a flareup which will identify the date of the flareups, which side and their pain level. This will be reviewed at each study visit.

Biospecimens are not kept by the investigators and are discarded once reviewed to confirm removal of pilosebaceous units.

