## 8.4 REPLACEMENTS

There will be no replacements if participants withdraw.

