# 9. STATISTICAL METHODS

## 9.1 SAMPLE SIZE ESTIMATION & JUSTIFICATION

Given that this is a pilot study assessing the effectiveness of FUE for HS management, we have decided 24 participants is required as a pilot. The result of this study will be used to inform sample size calculations for future studies as well as account for 20% rate of lost to follow-up.

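### The flare endpoint is a raw number over 24 weeks with no denominator for observed time, so if raw numbers are compared, shorter follow-up in one arm appears as fewer flares

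*Protocol*

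**What the plan says.** The flare endpoint appears in three places in the protocol, each time as a count.

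- Section 6.2, secondary objective 4: "To compare the number of disease flares between intervention and control group over 24 weeks".
- Section 2, synopsis, secondary objective ii: "To compare the number of disease flares between the treated and control groups for 24 weeks after treatment".
- Section 6.3, outcome measure 6: "Number of flare ups as well as location of flare ups".

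Flares are captured in a participant diary. Section 6.7 says of it: "This will be reviewed at each study visit". The diary form in Appendix 3 has columns for the date, location and pain of each flare. It has no field for the period that the diary covers. For the severity scores, section 6.4.1.8 states: "These assessments will be done at week 0, week 6, week 12 and week 24". After baseline, the scheduled reviews therefore fall at Weeks 6, 12 and 24.

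On early exit, section 8.4 states: "There will be no replacements if participants withdraw". Section 8.2.1 lists several grounds for withdrawal. One is the investigator's view that response to FUE is insufficient; another is an unsatisfactory effect of treatment. Leavers are encouraged to complete an unscheduled-visit evaluation. Section 9.1 says that the results will inform later sample sizes and also "account for 20% rate of lost to follow-up". Section 9.3 names paired t tests for lesion counts and scores and does not mention flares.

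**The concern.** A number of flares over a fixed 24 weeks is comparable between people only if each was observed for 24 weeks. Someone who leaves after the Week 6 review has had 6 weeks in which a flare could be recorded; someone who stays has had 24. The stated endpoint does not distinguish the two. This holds even if every flare is recorded perfectly while the participant is under observation.

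Two things are at stake. First, the comparison between arms: if one arm loses more people, or loses them sooner, a difference in follow-up can be read as a treatment effect. The protocol gives a reason to expect imbalance, because the insufficient-response ground refers to a procedure that only the intervention arm receives, in an unblinded trial. Second, the level of the flare figures: a count cut short by loss is too low, and section 9.1 intends the results for planning later studies.

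**Working it through.** **Inputs from the protocol.** 12 participants per arm (section 9.2); 24 weeks of follow-up with scheduled reviews at Weeks 6, 12 and 24; no replacement (section 8.4); a 20% loss figure (section 9.1).

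**Inputs assumed.** The protocol gives no flare rate, no timing of loss and no loss by arm. I assume a constant flare rate within participant, the same in both arms (true ratio 1), unrelated to leaving. Last observation is varied.

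**Plan's own figure.** There is none to reproduce: sections 9.1 and 9.2 give no flare rate, effect size, alpha or power.

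**Step 1: level of the count.** With a share d lost and last observation at week w, the share of flares missed is d × (1 − w/24). With d = 0.20:

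| Last observation | Calculation | Understated by |
|---|---|---|
| Week 0 | 0.20 × 1.00 | 20% |
| Week 6 | 0.20 × 0.75 | 15% |
| Week 12 | 0.20 × 0.50 | 10% |
| Week 18 | 0.20 × 0.25 | 5% |
| Week 24 | 0.20 × 0 | 0% |

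In whole participants, 20% of 24 is 4.8. Losing 4 gives 4/24 × 0.50 = 8.3% to 4/24 × 0.75 = 12.5%. Losing 5 gives 10.4% to 15.6%.

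**Step 2: ratio between arms.** Let kF and kC be the numbers lost in the FUE and control arms, and f = w/24 the fraction of follow-up observed in those lost. The apparent ratio is [(12 − kF) + kF·f] / [(12 − kC) + kC·f].

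| Lost, FUE vs control | Last observed Week 12 (f = 0.50) | Last observed Week 6 (f = 0.25) |
|---|---|---|
| 4 vs 1 | 10/11.5 = 0.87 | 9/11.25 = 0.80 |
| 3 vs 2 | 10.5/11 = 0.95 | 9.75/10.5 = 0.93 |
| equal numbers, equal timing | 1.00 | 1.00 |

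The direction follows the loss: with 1 vs 4 the ratios become 11.5/10 = 1.15 and 11.25/9 = 1.25.

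**Step 3: the same case as a rate.** Losing 4 vs 1 after Week 12 leaves 8 × 24 + 4 × 12 = 240 observed weeks with FUE and 11 × 24 + 1 × 12 = 276 with control; 240/276 = 0.87 is exactly the spurious ratio. Dividing each arm's flares by its own observed weeks gives 1.00.

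**Step 4: how often such splits arise by chance.** If 5 of 24 are lost irrespective of arm, a 3–2 split in either direction has probability 29,040/42,504 = 68%. The specific split of 4 FUE and 1 control has probability 495 × 12/42,504 = 5,940/42,504 = 14%.

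**The case against.** The strongest reply is that the protocol states an objective and does not prescribe an analysis of totals. A reader might infer that weeks without observation are to be counted as flare-free. No section says so. Section 9.3 specifies no flare analysis, and a statistical analysis plan that is not shown could use a rate or an offset. This stands as far as the model is concerned. It does not dispose of the point: whether the endpoint is a count or a rate belongs to its definition, and the protocol states a count three times. Nor can a later analysis plan recover coverage dates that the diary never asked for; visit dates would be only a proxy.

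Other parts of the reply also stand.

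- **The 20% figure.** A reader might infer that 20% loss is expected in this trial. The sentence in section 9.1 can equally refer to future studies. Section 6.4.1.1 gives 20 participants, and 20 × 1.2 = 24 fits the first reading without proving it.
- **Recovered weeks.** The unscheduled evaluation at withdrawal, dated diary entries and the review of progress at each visit may recover flares after the last scheduled review. Week 6 and Week 12 are therefore scenarios, not fixed cut-offs.
- **Completers.** Section 8.3.5 defines completion as follow-up to Week 24. Under the constant-rate assumption used here, the mean count among completers is unbiased. It loses precision, and it becomes unreliable if leaving is related to flares.
- **Chance splits.** With arm-blind loss the commonest outcome is 3–2, where the distortion is small for 12 per arm. The 4–1 case matters mainly because one withdrawal ground applies to one arm only.

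**Conclusion.** The point holds in a limited form. The flare endpoint is fixed as a raw number over 24 weeks without a denominator for observed time, in a trial that foresees early exits, does not replace them and has an arm-specific ground for withdrawal. Compared literally, it favours the arm with shorter observation.

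The size depends on assumptions that the protocol does not settle. The illustrated bias in the ratio runs from 5–7% (3 vs 2 lost) to 13–20% (4 vs 1 lost) and requires unequal loss or unequal timing. With equal loss and timing only the absolute levels, and the absolute difference, shrink. It would be tempting to say that the flare burden will be understated by 10–15%. The protocol does not support that as a fact: it needs 20% loss, a raw total, a constant rate and last observation averaging Week 6 to 12.

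This is a secondary endpoint of a 24-person pilot with no power claim, so the consequence is moderate. The change is worth making because it is cheap and the coverage dates cannot be collected afterwards.

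**What to change.** Restate secondary objective 4, synopsis objective ii and outcome measure 6 as flares per week of observed diary coverage. Count coverage in both arms from Week 0 (Visit 1) to the last reviewed diary, including one reviewed at a withdrawal visit, or to Week 24.

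In section 9.3, add that all randomised participants are compared by a rate ratio with a confidence interval, from a simple count model with log observed weeks as offset. Report observed weeks per arm beside it. Add to the visit record the last date covered by the diary, so that a blank diary can be told from one not kept.

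The cost is rewording in sections 2, 6.2, 6.3 and 9.3 and one date field per visit, with no extra visits or participants. The limitation is that the offset assumes a roughly constant flare rate within participant and does not remove bias if those who flare most are the ones who leave. Withdrawals by reason and arm should therefore be reported next to the rate ratio.

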### 6.4 STUDY TYPE & DESIGN & SCHEDULE

#### 6.4.1 STUDY ASSESSMENTS

##### 6.4.1.1 SUBJECT DEMOGRAPHICS

Demographic and baseline characteristics to be collected on participants include: Date of birth, gender, ethnicity and child-bearing potential (for females only).

20 participants will be recruited and divided into intervention and controlled group in a 1:1 ratio.

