##### 6.4.1.2 MEDICAL HISTORY

Medical history and current medical conditions will be collected. Only data up to 6 months prior to signing of the informed consent and until the start of study treatment is required. Whenever possible, diagnoses and not symptoms will be recorded.

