##### 6.4.2.1 SCREENING

All participants will be screened prior to enrolment in the study. The following procedures must be conducted at the screening visit.

- Written informed consent
- Review of eligibility (diagnosis, inclusion and exclusion criteria)
- Medical history (including previous psoriasis treatments)
- Physical Examination
- Vital Signs (Respiratory rate, heart rate, tympanic temperature, blood pressure)
- Weight
- Height
- HS severity score baseline measurements

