## 9.2 POWER CALCULATIONS

This pilot study uses 12 participants in each group (intervention vs controlled) and results from this will allow us to calculate the sample size required for statistical power in future clinical studies.

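### The between-arm flare comparison has no pre-treatment flare count, so with 12 per arm it is less precise than one screening question could make it

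*Protocol*

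**What the plan says.** Flares are a between-arm endpoint. The fourth item under Study Aims (Protocol 6.2) is "To compare the number of disease flares between intervention and control group over 24 weeks", and Protocol 6.3 lists "Number of flare ups as well as location of flare ups" among the outcome measures. They are recorded on a participant diary (6.7 and Appendix 3), which is reviewed at study visits.

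The places where a pre-treatment count could stand do not contain one:

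- 6.4.1.1 limits the listed baseline characteristics to date of birth, gender, ethnicity and child-bearing potential.
- 6.4.1.2 opens a look-back window: "Only data up to 6 months prior to signing of the informed consent and until the start of study treatment is required". It asks for diagnoses in preference to symptoms and mentions no flare count.
- 6.4.2.1 takes "HS severity score baseline measurements". The Week 0 visit and the Appendix 2 schedule likewise take scores and a review of progress.
- No start of the diary before treatment is stated. Screening and Week 0 may be the same day (6.4.2.2), so no run-in diary is assured.

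Entry (7.2) requires active disease but no minimum flare frequency. The randomisation section (6.6) names no stratification factor. On size, 9.2 states "This pilot study uses 12 participants in each group (intervention vs controlled").

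**The concern.** A count over 24 weeks in two groups of 12 is an imprecise endpoint if people differ in how often they flare. Their own earlier flare count is then a natural covariate, and the look-back window already open in 6.4.1.2 is about as long as follow-up. Without it, the flare comparison carries between-patient variation that could have been removed, and the baseline table cannot show whether the arms started with similar flare histories.

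The pilot's stated purpose adds to this. Its results are meant to inform the size of later studies (9.1, 9.2). Without prior counts it cannot estimate the correlation between flares before and after treatment, which is what one would need to size a later trial with an adjusted flare analysis.

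**Working it through.** **The plan's own figure.** Protocol 9.1 says "we have decided 24 participants is required as a pilot". No significance level, power, effect size, standard deviation or flare rate is given, so the number cannot be reproduced. Only 24 / 2 = 12 per arm checks. 9.1 also says the sample size is to "account for 20% rate of lost to follow-up", which leaves 24 × 0.8 = 19.2, or about 9 to 10 per arm. Separately, 6.4.1.1 says "20 participants will be recruited and divided into intervention and controlled group in a 1:1 ratio", which would be 10 per arm. That conflict is a different matter, but it makes 10 per arm a useful second case.

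**Window.** 24 weeks × 7 = 168 days, which fits inside a 6-month look-back.

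**Why a prior count helps.** Assume each person has a flare rate with mean μ per 24 weeks and gamma variation with squared coefficient of variation k, and that the rate is the same before and after. Then:

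- Var(count) = μ + kμ²
- Cov(prior, later) = kμ²
- correlation ρ = μk / (1 + μk)

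The variance of the adjusted arm difference falls by roughly ρ². For μ = 4 and k = 0.6, ρ = 2.4 / 3.4 = 0.71 and ρ² = 0.50; simulation on raw counts gives a cut of 0.49. For μ = 2 and k = 0.3, ρ = 0.6 / 1.6 = 0.375 and ρ² = 0.14; simulation gives 0.12.

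**Power, 12 per arm, true rate ratio 0.5.** The outcome is log(1 + flares), analysed without and then with log(1 + prior flares), 1,500 simulated trials per setting. Gamma shape 1 means a coefficient of variation of 1.0; shape 2 means 0.7. The period-noise columns multiply each period's rate by an extra gamma factor with variance 0.4.

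| Mean flares, shape | Stable: without | Stable: with | Period noise: without | Period noise: with |
|---|---|---|---|---|
| 3, shape 1 | 0.230 | 0.355 | 0.191 | 0.222 |
| 3, shape 2 | 0.329 | 0.410 | 0.227 | 0.253 |
| 6, shape 1 | 0.245 | 0.531 | 0.197 | 0.263 |
| 6, shape 2 | 0.405 | 0.616 | 0.299 | 0.326 |

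A repeat run put the period-noise range at 0.17-0.27 without and 0.22-0.32 with the covariate, so the summary range is about 0.17-0.30 to 0.22-0.33. The standard error under no effect falls by at most 1 − 0.231/0.369 = 37% and at least 1 − 0.303/0.313 = 3%.

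**Wider grid.** Means 2, 4 and 6, k = 0.3, 0.6 and 1.0, stable rates, 20,000 trials each:

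- 12 per arm: the variance of the arm difference on the log scale falls by 8% to 64%, and power rises from 21-54% to 28-68%.
- 10 per arm: the variance falls by 6% to 63%, and power goes from 18-47% to 23-59%. In the weakest setting (mean 2, k = 0.3) it stays at 29%.

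**Validity without the covariate.** In the same grid with no true effect and 12 per arm, the unadjusted test on log(1 + flares) rejects in 4.7% to 5.4% of trials. The observed flare ratio is nevertheless 0.67 or lower in favour of FUE in 8% to 21% of trials, and 0.5 or lower in 1% to 9%. That is sampling error, which a proper interval reflects.

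**The case against.** A reader might infer that chance differences in flare-proneness would be mistaken for an FUE effect and that nothing recorded could reveal them. The documents do not support that. Allocation is random, and a test that reflects between-patient variation keeps its level, as the 4.7-5.4% shows. A Poisson test that ignores this variation would not (12-45% in the same grid), but the protocol names no such test for flares. Nor is imbalance wholly invisible: lesion counts and Hurley stage (6.4.1.8), severity scores at screening and Week 0, phenotype (6.4.1.5) and treatments in the prior 6 months (6.4.1.3) are all recorded. They are partial substitutes only. The lesion counts and scores are snapshots, and 6.4.1.6 allows medication to prevent flares before FUE, which may depress them.

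Three further points stand. The protocol contains no figure on how much flare rates vary or what predicts them, so calling the prior count a strong covariate is an assumption, and the gain may be small. Flares are one secondary endpoint of a pilot that claims no power. And the choice of covariate is commonly left to an SAP. The last point does not settle the matter, because an SAP cannot adjust for data the visits never collect.

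The most practical objection concerns timing. The list is made before recruitment, the participant number fixes the arm (6.6), and 6.4.2 has that number assigned after consent, while screening evaluations also follow consent. The trial is open-label. A count recalled once the arm is known could differ by arm, and adjusting for it could introduce bias that is absent now. This stands, and the fix must deal with it.

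**Conclusion.** The point holds as a loss of precision. No pre-treatment flare count is planned, and the between-arm flare comparison is therefore less precise than it could cheaply be. It is not a source of bias, and an unadjusted analysis that reflects between-patient variation remains valid.

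The benefit depends on how stable a person's flare rate is, which the protocol does not tell us. It is substantial if rates are stable and slight if they vary strongly between periods. Even the best setting examined stays below 70% power for a halving, so the covariate improves the estimate without making the flare comparison confirmatory. The change is worth making because it costs little and because the count cannot be collected as cleanly once participants know their arm.

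**What to change.** - **6.4.2.1 (Screening):** add the number and location of flares in the 24 weeks before Week 0, by participant report checked against clinic notes, with the same flare wording as the Appendix 3 diary. The diary sheet does not itself define a flare, so one wording should serve both. Where screening falls before Week 0 (up to 28 days are allowed), end the 24-week window on the day of the count.
- **6.4.2 (Study schedule):** amend the order so that this count is recorded after consent but before the participant number that fixes the arm is assigned.
- **9.3:** compare flares between arms with log(1 + prior flares) as covariate, and show the prior count by arm in the baseline table.

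The cost is one case report form item, one change of sequence, one analysis sentence and one degree of freedom. Recall error, and any flare-preventing medication given before FUE, will reduce the gain. Recall error cannot favour an arm if the count is taken before the arm is known.
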